8.5.1.2. Sample Size Methods and Assumptions

The proportion of SND diagnoses in bradycardia subjects is currently unknown within the study geographies. The PANARM HF study of 2000 subjects found that 146 out of 331 bradycardia subjects (44%) had symptomatic SND and that 15 (10%) of SND subjects opted for IPG therapy (internal data on file). The power calculations conservatively assume that the SND diagnosis will be 20% at six months of follow-up, or equivalently an SND incidence of 0.4 diagnoses per person-year. Thus, the margin of error will be $\pm 4\%$ in a sample of 500 subjects per geography/country, based on a 95% confidence interval. If 500 subjects are collected in Phase I and 1000 subjects are collected in Phase II, assuming a type I error of 0.05 and power of 0.90, a chi-square test will detect an increase in SND diagnosis of at least 8%. For example, the study will find a statistically significant difference between a Phase I SND percentage of 20% at 6 months and a Phase II SND percentage of 28% at 6 months. The Poisson regression for the same scenario has a power of 0.95 to compare SND incidence of 0.4 versus 0.56 diagnoses per person-year. If the proportion of SND diagnoses is smaller than 20%, there will be more power to detect significant differences in the diagnosis proportion. Thus, the Phase II sample size will be recalculated within geography/country once Phase I data collection is complete. It is expected that the study attrition rate may be 10-15% of the study population. To account for attrition, *the sample size for Phase I will be 550 subjects per geography/country and for Phase II may be 1100 subjects per geography/country.*

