1. 90% power and type I error of 0.05
2. Phase I enrolled 500 subjects with complete follow-up
3. Overall goal is 2:1 sampling for Phase II versus Phase I
4. Calculation via methods in Fleiss JL, Tytun A, Ury HK (1980): A simple approximation for calculating sample sizes for comparing independent proportions. *Biometrics* 36:343–6.

Table 2. Subjects Required to Observe Changes in SND Diagnosis

SND % Phase I	SND % Phase II	Phase II Subjects	Higher SND % Phase II	Phase II Subjects
------------------	-------------------	----------------------	--------------------------	----------------------

This document is electronically controlled. Printed copies are considered uncontrolled.

Confidential

10%	20%	N=405	25%	N=203
20%	30%	N=593	35%	N=279
30%	40%	N=717	45%	N=327
40%	50%	N=778	55%	N=347
45%	55%	N=785	60%	N=346
50%	60%	N=776	65%	N=338
60%	70%	N=711	75%	N=302
70%	80%	N=582	85%	N=237
80%	90%	N=390	95%	N=144

There is clear power to attain the first primary objective with 873 subjects or fewer in Phase II, accounting for 10% attrition.

Section 4.2 Primary objective #2 for IPG implants

Scenario 1 -- Additional assumptions:

1. No change in SND diagnosis between Phase I and Phase II, i.e., the first primary objective is not met.
2. Futility is assumed when more than 1000 subjects with complete follow-up are needed for Phase II. Areas of futility are not included in **Error! Reference source not found.** and **Error! Reference source not found..**

Table 3. For SND diagnosis rates less than 50%

	IPG % Phase I	IPG % Phase II	Phase II Subjects Needed	Accounting for Attrition	CI width for IPG % with Half of Phase II Data
10% SND = 50 SNDs	80%	95%	>1000	>1000	0.06
	85%	100%	856	952	0.03
20% SND = 100 SNDs	5%	20%	769	855	0.18
	10%	25%	1013	1126	0.17
	15%	30%	>1000	>1000	0.16

This document is electronically controlled. Printed copies are considered uncontrolled.

Confidential

	70%	85%	>1000	>1000	0.07
	75%	90%	968	1076	0.07
	80%	95%	717	797	0.06
	85%	100%	428	476	0.03
30% SND = 150 SNDs	5%	20%	513	570	0.18
	10%	25%	676	752	0.17
	15%	30%	814	905	0.16
	20%	35%	929	1033	0.16
	25%	40%	1021	1135	0.15
	30%	45%	>1000	>1000	0.15
	55%	70%	>1000	>1000	0.14
	60%	75%	1004	1116	0.14
	65%	80%	908	1009	0.13
	70%	85%	788	876	0.13
	75%	90%	645	717	0.12
	80%	95%	478	532	0.10
40% SND = 200 SNDs	85%	100%	286	318	0.08
	5%	20%	385	428	0.18
	10%	25%	507	564	0.17
	15%	30%	611	679	0.16
	20%	35%	697	775	0.16
	25%	40%	766	852	0.15
	30%	45%	817	908	0.15
	35%	50%	850	945	0.15

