8.5.1.1. Analysis Methods

A. Statistical Methodology

To compare the proportion of subjects with an SND diagnosis pre-intervention (Phase I) to the proportion post-intervention (Phase II), a chi-square test will determine statistical significance. The proportion of subjects diagnosed will be evaluated at multiple time points because the time to diagnosis is expected to vary by geography. Thus, times are pre-specified starting at 6 months and any additional 6-month interval thereafter for which there is sufficient follow-up data available to compare study phases.

Proportions calculated at all available time points will be reported. Additionally a Poisson regression will compare the average number of subjects with an SND diagnosis in Phase I and Phase II where the subject time in study is treated as an offset in the model. The above described tests will be performed only for subjects in the South Asia geographical region as per section 6.

[REDACTED]

[REDACTED]

This document is electronically controlled. Printed copies are considered uncontrolled.

Confidential

[REDACTED]

[REDACTED]

[REDACTED]

B. Determination of Patients/Data for Analysis

All subjects that are enrolled in the study will be included in the determination of the proportion estimates. The proportion estimates will be calculated based on information from fixed time points at 6 months of follow-up, 12 months of follow-up, and any additional 6-month interval thereafter for which there is sufficient follow-up data available to compare study phases. The number of subjects that obtain an SND diagnosis by pre-specified time point $t = 6, 12, \text{ etc.}$, is included in the numerator and the number of subjects enrolled is included in the denominator.

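### The 0.95 Poisson power stated for Primary Objective 1 does not follow from its six-month scenario, which gives about 0.80 to 0.88 with model-based errors

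*SAP*

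**What the plan says.** SAP 8.5.1.2 sets one scenario, and protocol 11.1 (Primary Objective #1) repeats it.

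- **Sample size:** "If 500 subjects are collected in Phase I and 1000 subjects are collected in Phase II".
- **Phase I rate:** the assumption is that "the SND diagnosis will be 20% at six months of follow-up, or equivalently an SND incidence of 0.4 diagnoses per person-year".
- **Contrast:** the example compares "a Phase I SND percentage of 20% at 6 months and a Phase II SND percentage of 28% at 6 months".
- **Chi-square test:** "assuming a type I error of 0.05 and power of 0.90, a chi-square test will detect an increase in SND diagnosis of at least 8" per cent.
- **Poisson regression:** "The Poisson regression for the same scenario has a power of 0.95 to compare SND incidence of 0.4 versus 0.56 diagnoses per person-year".

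SAP 8.5.1.1 describes the Poisson model as one "where the subject time in study is treated as an offset in the model". Enrolment is then raised to 550 and 1100 because "It is expected that the study attrition rate may be 10-15% of the study population". The Poisson figure comes with no other follow-up time, no sidedness and no variance assumption.

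**The concern.** With equal six-month exposure, the Poisson model and the chi-square test use the same 100 and 280 diagnoses. The Poisson variance is larger than the binomial variance of a yes/no outcome, so the Poisson test should have the lower power. The plan gives it the higher power.

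The change in diagnoses per person-year is part of the Primary Objective 1 endpoint (SAP 4.1.1.1), and the Poisson regression is its test. A reader of the SAP would expect a 5% chance of missing the planned effect with it. In the stated scenario that chance is roughly 12% to 20%. The reader would also take the Poisson for the stronger test, and could misread a non-significant Poisson result beside a significant chi-square.

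**Working it through.** **Inputs (SAP 8.5.1.2).** n1 = 500, n2 = 1000, p1 = 0.20 and p2 = 0.28 at six months, rates 0.4 and 0.56 per person-year, type I error 0.05. Equating 20% at six months with 0.4 per person-year implies 0.5 person-year per subject.

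**Sidedness.** It is not written beside the Poisson figure. The row of SAP Table 2 (Section 7) that reads "20% 30% N=593 35% N=279" settles the convention. For 20% versus 30%, a two-sided calculation without continuity correction gives 594 Phase II subjects, and a one-sided one gives 482. I therefore use two-sided 0.05.

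**The plan's chi-square figure.** Pooled p = 380/1500 = 0.2533.
- Null SE = sqrt(0.2533 × 0.7467 × (1/500 + 1/1000)) = 0.02382.
- Alternative SE = sqrt(0.16/500 + 0.2016/1000) = 0.02284.
- Power = Φ((0.08 − 1.96 × 0.02382)/0.02284) = 0.93.
- The detectable difference at 90% power is 7.6 points, so the plan's 8 checks.

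**The plan's Poisson figure.** Expected events are 500 × 0.5 × 0.4 = 100 and 1000 × 0.5 × 0.56 = 280.
- Log rate ratio = ln(0.56/0.4) = ln 1.4 = 0.3365.
- SE = sqrt(1/100 + 1/280) = 0.1165.
- z = 0.3365/0.1165 = 2.89.
- Power = Φ(2.89 − 1.96) = **0.82**, against the stated 0.95.

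**Other methods and readings, 500/1000 subjects, six months, two-sided:**

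| Method | Power |
|---|---|
| Poisson-regression sample-size formula, Phase I as baseline | 0.80 |
| Wald formula, log rate ratio | 0.82 |
| Score formula | 0.84 |
| Simulated Poisson counts (Wald, likelihood ratio) | 0.84, 0.85 |
| Simulated yes/no diagnosis, 0.5-year offset (Wald, likelihood ratio) | 0.87, 0.88 |
| Exposure stopped at diagnosis, rates 0.4 and 0.56 (formula, simulated) | 0.78, 0.80 |
| Exposure stopped at diagnosis, hazards matched to 20% and 28% (formula, simulated) | 0.91, 0.92–0.93 |
| Chi-square test | 0.93 |

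The matched hazards are −ln(0.80)/0.5 = 0.446 and −ln(0.72)/0.5 = 0.657 per person-year, a ratio of 1.47. These are not the plan's stated rates.

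**What would give 0.95.** With t years per subject the events are 200t and 560t. Setting 0.3365/sqrt(1/(200t) + 1/(560t)) = 1.96 + 1.645 gives t = 0.78 year. At six months the equivalent is about 779 and 1,558 subjects. The enrolled 550/1100 at six months gives only 0.86, and the extra subjects are there for attrition. A one-sided test gives 0.89 by the Wald formula and about 0.935 when simulated with yes/no outcomes.

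**Standard errors.** For a yes/no outcome with equal exposure, the robust SE is sqrt(0.80/100 + 0.72/280) = 0.1028. The model-based SE is 0.1165/0.1028 = 1.13 times that, about 13% too wide. With 20% in both phases, the simulated type I error is 0.028 model-based and about 0.05 robust. Robust power is 0.905 by formula and 0.92 simulated.

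**The case against.** The strongest reply is that the offset is each subject's time in study, not a fixed six months. Protocol 4.3 enrols Phase I for about 12 months and Phase II for about 18 months, and collects diagnostic data until 6 months after the last enrolment. Under uniform accrual (an assumption), potential follow-up is 0.5 to 1.5 years and 0.5 to 2.0 years. Simulated at rates 0.4 and 0.56 with exposure stopped at diagnosis, mean exposure is 0.81 and 0.87 year and power is about 0.97. With dropout of 0.12 per year it is about 0.956.

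This stands to the extent that a reader might infer from the six-month shortfall that the planned analysis itself lacks power. The documents do not support that inference, because the analysis may accrue more exposure than the scenario assumes. But it does not make the printed figure right. The sentence ties 0.95 to the six-month scenario, and the accrual calculation assumes a constant rate and no early exits. Protocol 5.7 and the completion criteria in SAP Section 5 let subjects leave once found not indicated or not receiving pacing, which shortens exposure.

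A reader might also infer that a Poisson model can never match the chi-square test, or that 0.82 is the one correct replacement. Neither holds. The first is true only with equal fixed exposure: with matched hazards and exposure stopped at diagnosis, the two tests are about level. On the second, 0.82 is a formula value for Poisson counts, and a yes/no outcome gives about 0.87.

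Text is redacted directly after the Poisson description in SAP 8.5.1.1, so it cannot be said that the variance method is unspecified.

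The consequence is also limited. SAP 4.1 calls the study exploratory, the Poisson regression is additional to the chi-square test, and SAP 8.4 calls the Phase II calculations preliminary.

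**Conclusion.** The stated 0.95 is wrong for the scenario to which the text attaches it. With 500 and 1000 subjects, six months of exposure each, rates of 0.4 and 0.56, two-sided 0.05 and model-based errors, power is about 0.80 to 0.88. That is 7 to 15 points short of the stated figure and below the chi-square test's 0.93. Stopping exposure at diagnosis gives 0.80 or 0.91 to 0.93, depending on which rates are held, and does not reach 0.95 either.

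The conclusion rests on the two-sided convention inferred from SAP Table 2 and on reading the same scenario as six months per subject. It covers the printed power figure and its documentation. It does not show that the trial is too small.

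**What to change.** In SAP 8.5.1.2 and protocol 11.1, do one of two things:

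- Replace 0.95 with the recomputed six-month power and name the method: 0.82 by the Wald formula, or about 0.87 by simulation for a yes/no outcome.
- Keep 0.95, drop the claim that it describes the same scenario, and state the mean exposure behind it (about 0.78 year per subject at full exposure), with the accrual and early-exit assumptions that support it.

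In either case, state that the test is two-sided and whether exposure stops at diagnosis.

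In SAP 8.5.1.1, if the redacted text does not already do so, specify robust (sandwich) standard errors for the Poisson model. With equal fixed exposure this brings the type I error from about 0.028 to about 0.05 and power to about 0.92.

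The cost is one corrected sentence in each document and at most one option in the analysis code. No subjects are added and 550/1100 stands. The printed power becomes less favourable if the first option is taken.

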This section has been added to this study SAP following the completion of Phase I in all geographies. While the initial investigation plan intended for the study to be conducted in two phases across multiple geographies, only one geography has opted to complete both phases of the study. The geographies that have completed Phase I of the study are CEE, Latin America and South Asia. Only South Asia has proceeded into Phase II of the study with sites in both India and Bangladesh participating in both phases. CEE and Latin America both terminated their participation in IMPROVE Brady after completing Phase I of the study. Accordingly, planned statistical analyses that were going to investigate study objectives within geography or country can no longer be performed. Therefore, for any analysis comparing phases, it will be performed on the South Asia geography only. Analyses by site within the South Asia geography will only include sites enrolling in both Phase I and Phase II.

This document is electronically controlled. Printed copies are considered uncontrolled.

Confidential

7. Determination of Sample Size

Calculations of Phase II Sample Size Adaptation

The planned sample size in Phase II is up to 1100 enrollments. This sample size assumes that, in Phase I, 20% of enrolled subjects obtain an SND diagnosis and that 10% of subjects with an SND diagnosis then go on to receive indicated therapy with an IPG. This sample size also assumes that 10% of enrolled subjects will be lost to follow-up. The sample size in Phase II will be adapted, however, if the results from Phase I within each geography differ from the original assumptions about diagnosis and implant rates. The adaptation is described below.

Summary

Enrolling 500 subjects in Phase I and 1000 subjects with complete follow-up in Phase II powers the study to detect increases in the SND percentage of 9% or greater. The study is also powered to detect an increase in the IPG implant percentage by 15%. This assumes that the Phase I SND percentage is 20% or greater and that the percent of diagnoses does not decrease in Phase II.

Synopsis of Phase II Preliminary Power and Sample Size Calculations

For Phase II, we will outline many different possible scenarios and the sample sizes required for each. Actual Phase II calculations will depend on what is observed in Phase I within each geography.

Section 4.1 Primary objective #1 for SND

The following assumptions are made for all calculations.

Assumptions:

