8.2. General Methodology

8.2.1. Special Considerations

The study will have an enrollment restriction. The maximum number of subjects to be enrolled at any given study center is 20% of the expected sample size in that geography; 20% of 1650 subjects equals 330 subjects per study center.

Sample size calculations will account for an attrition rate in the study of 10%.

An analysis will be built to examine temporal confounding. Since the study design does not randomize the treatment and control subjects it is possible that the time elapsed over Phase I and Phase II of the study will confound the results. To examine the possibility of temporal confounding, an interrupted time series regression analysis will be performed. This analysis will adapt Rubin's causal model for rate parameters.

This document is electronically controlled. Printed copies are considered uncontrolled.

Confidential

Rubin's causal model for linear outcome Y is $Y = \beta_0 + \beta_1 X + \beta_2 D$, where X is time and D is a dummy variable for group assignment, before and after intervention. To adopt this model for rate parameters estimated in the primary objectives of the study, the model to be fit is $\log(Y) = \beta_0 + \beta_1 X + \beta_2 D + \log(Z)$ where Y is a binary response to indicate an SND diagnosis and Z is the amount of subject follow-up. The same model will also be fit to model the rate of IPG treatment. If an association is seen by testing β_1 , then temporal confounding exists.

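### The 550/1100 enrolment targets cover about 9% attrition, not the stated 10-15%, and the SAP uses two attrition rates and two inflation formulas; the stated 90% power is nevertheless essentially kept.

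*SAP*

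**What the plan says.** SAP 8.5.1.2 builds the first primary objective on 500 and 1000 subjects: "If 500 subjects are collected in Phase I and 1000 subjects are collected in Phase II", with type I error 0.05 and power 0.90, the design detects an 8-point rise in SND diagnosis (20% to 28%). It then says "It is expected that the study attrition rate may be 10-15% of the study population" and gives 550 and 1100 per geography or country as the sizes that allow for this. Protocol 11.1 carries the same text.

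Elsewhere the SAP uses a single rate:

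- Section 7, opening paragraph: "This sample size also assumes that 10% of enrolled subjects will be lost to follow-up".
- Section 7, text after Table 2: "873 subjects or fewer in Phase II, accounting for 10% attrition".
- Section 8.2.1: "Sample size calculations will account for an attrition rate in the study of 10" (per cent).

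Section 7 also makes clear that the base numbers are subjects with follow-up, not enrolments. Its Summary says "Enrolling 500 subjects in Phase I and 1000 subjects with complete follow-up in Phase II powers the study", and the assumptions for Table 2 include "Phase I enrolled 500 subjects with complete follow-up". The Summary adds that the design is powered for a 15-point rise in the implant percentage.

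**The concern.** An attrition allowance should return the number that the power calculation needs once losses at the assumed rate have occurred. That number is 500/1000. The enrolment targets look like a multiplication by 1.10, which falls short of 500/1000 at any attrition above about 9%, and so across the whole 10-15% range given in the sentence before them.

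Two things follow. A reader cannot tell which attrition rate underlies the reported power. And the Phase II size is to be recalculated after Phase I, which needs one defined rate and one formula, where the SAP offers two of each.

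**Working it through.** **Inputs.** 500/1000 subjects, attrition 10-15%, enrolment 550/1100, 20% versus 28% for objective 1, and 10% versus 26% among SND subjects for objective 2 (SAP 8.5.1.2 and 8.5.2.2). The 10% rate is from SAP 7 and 8.2.1. The documents do not say whether the tests are one- or two-sided; two-sided 0.05 is assumed here.

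**1. Reproducing the plan's figures.**
- Headline: 500 × 1.10 = 550 and 1000 × 1.10 = 1100. These match exactly.
- Tables: 785 / 0.90 = 872.2, given as 873 after Table 2. In Table 3, 856 / 0.90 = 951.1, given as 952, and 1013 / 0.90 = 1125.6, given as 1126. Multiplying by 1.10 would give 863.5, 941.6 and 1114.3, which do not match.

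So the headline uses n × (1 + d), while the section 7 text and tables use n / (1 − d).

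**2. What 550/1100 delivers.**

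| Attrition | Subjects remaining | Shortfall from 500/1000 | Enrolment needed, n/(1−d) |
|---|---|---|---|
| 10% | 495 / 990 | 5 / 10 (1%) | 556 / 1112 |
| 15% | 467.5 / 935 | 32.5 / 65 (6.5%) | 589 / 1177 |

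Break-even attrition: 1 − 500/550 = 0.091.

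**3. Objective 1 on subjects remaining, 20% versus 28%.** Power = Φ[(Δ − 1.96·SE₀)/SE₁], where SE₀ uses the pooled proportion (0.20 + 2 × 0.28)/3 = 0.2533 and SE₁ the separate ones.
- 500/1000: SE₀ = √(0.18916 × 1.5/500) = 0.02382; SE₁ = √(0.16/500 + 0.2016/1000) = 0.02284; power 0.928.
- 495/990: power 0.925.
- 467.5/935: SE₀ = 0.02464; SE₁ = 0.02362; power 0.910 (0.899 with continuity correction).

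The plan has slack: 451/902 already gives 90% power, or 470/940 with continuity correction.

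**4. Objective 1 on the planned denominator.** SAP 8.5.1.1 divides by all enrolled subjects, so losses dilute the proportions and do not shrink the sample. Assume that every lost subject counts as undiagnosed and that the loss rate is equal in both phases:
- 10%: 0.20 × 0.90 = 0.180 versus 0.28 × 0.90 = 0.252 in 550/1100; power 0.917.
- 15%: 0.20 × 0.85 = 0.170 versus 0.28 × 0.85 = 0.238 in 550/1100; power 0.897.

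**5. Objective 2, exact two-sided Fisher test.** The plan assumes that 20% are diagnosed, which gives 100/200 SND subjects from 500/1000. After attrition this is 0.20 × 495 = 99 and 0.20 × 990 = 198, or 0.20 × 467.5 = 93.5 (taken as 94) and 0.20 × 935 = 187.

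| SND subjects | 10% vs 26% | 10% vs 25% |
|---|---|---|
| 100 / 200 | 0.923 | 0.890 |
| 99 / 198 | 0.920 | 0.886 |
| 94 / 187 | 0.900 | 0.863 |

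The last column is the 15-point claim in the section 7 Summary. SAP Table 3 agrees that it is not met: at 20% SND, going from 10% to 25% needs 1013 Phase II subjects, or 1126 with attrition, against 1000 and 1100 planned.

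**The case against.** The best case for leaving the text alone has four parts.

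- **The power statements of 8.5.1.2 and 8.5.2.2 survive.** Even at 15% attrition the two worked scenarios keep 0.910 and 0.900. The 9-point diagnosis increase in the section 7 Summary keeps 0.959 at 467.5/935. This stands.
- **At 10% the gap is close to rounding.** It is 5 in 500 and 10 in 1000, and the targets are worded as approximate in several places. This stands too; only the upper part of the 10-15% range gives a shortfall worth stating.
- **10% and 10-15% need not conflict.** The first can be read as the planning value and the second as a hedged expectation that starts there. That softens the difference in rates. It does not explain why 550/1100 is presented as the allowance for the range, nor why the headline and the tables use different formulas.
- **The size is provisional or past.** Phase II is to be recalculated, and SAP version 3.0 was written after Phase I had finished, so the 550 can no longer change. This rules out a change of target, not a correct description of what the target provides.

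Three stronger readings are tempting and not supported. A reader might infer that attrition leaves the study underpowered for its worked examples; steps 3 to 5 show that it does not. A reader might blame attrition for the failed 15-point implant claim; power is 0.890 at the full 100/200, so attrition only worsens an existing shortfall. And a reader might take the 468/935 figures as describing the objective 1 analysis, which in fact keeps every enrolled subject in the denominator.

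**Conclusion.** The point holds as an inconsistency in the stated sample size, of low severity. As written, 550/1100 allows for about 9% attrition and misses 500/1000 by 1% at 10% and by 6.5% at 15%. The SAP carries two attrition rates and two inflation formulas.

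The stated 90% power is essentially kept for 20% versus 28% and for 10% versus 26%. The lowest value found for these is 0.897, for objective 1 on all enrolled subjects at 15% attrition. It rests on two-sided testing, equal loss in both phases and every lost subject counted as undiagnosed. The objective 2 values rest on the plan's 20% diagnosis rate.

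The 15-point implant claim is a separate error. It is contradicted by the SAP's own Table 3 and is slightly below 90% power before any loss.

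**What to change.** Leave enrolment unchanged and correct the text:

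1. State one attrition range in Protocol 11.1 and SAP 7, 8.2.1 and 8.5.1.2, and use n / (1 − d) throughout.
2. Say that 550/1100 covers about 9% attrition and yields 468-495 and 935-990 subjects with complete follow-up over 10-15%.
3. For objective 1, report power on the all-enrolled denominator for 20% versus 28%: 0.917 at 10% and 0.897 at 15%, naming the assumption that lost subjects count as undiagnosed.
4. For objective 2, report exact Fisher power for 10% versus 26%: 0.920 at 99/198 and 0.900 at 94/187.
5. Correct the section 7 Summary on the 15-point implant increase. Either restate it as 16 points, in line with 8.5.2.2, or give its power: 0.890 before attrition, and 0.886 to 0.863 after it.

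The cost is wording only: no added patients and no change to design or analysis.
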